#### 5.4 Randomization

Treatment order will be block randomized by a member of the Center for Cognitive Medicine within the Department of Psychiatry at VUMC who is not otherwise involved in this study. All investigators and subjects will be blinded to treatment order.

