performed in 5 blocks of 32 trials, with 3 emotional blocks with angry/fearful/sad/disgust faces and 2 non-emotional blocks (Figure 1). Each stimulus is presented for 1 s with a 1 s interstimulus interval. In each block the subject is instructed on the go/no-go targets, each comprising 50% of the task stimuli, with instructions changing at the halfway point in each block. Each block contains two instructions. For example: Emotional blocks: go-angry/nogo-fear or go-fear/nogo-angry; Non-emotional blocks: go-male/nogo-female or go-female/nogo-male (Figure 2). Error rates and reaction times are recorded.

Figure 2 Emotional Go/NoGo schematic. Subjects are given a target instruction at the start of each block for 6 seconds. There is 1 second of blank screen between each 1 second stimulus presentation. In this schematic, the subject would press a key ("Go") when presented with the first stimulus (angry; green border represents the correct response is "Go". This border would not be present in the actual task), and withhold pressing a key for the second stimulus (sad; red border).

Subjects will be monitored for at least 30 minutes after patch removal to confirm the absence of side effects that would compromise their safety upon leaving the hospital.

Subjects will return for day 2 of testing not less than 5 days following day 1. On day 2, subjects will receive the treatment they did not receive on day 1. They will be asked a series of standard questions to assess for the presence of any side effects following their initial study day. If female, they will again be administered a urine pregnancy test to confirm the absence of pregnancy. The remainder of the procedure will be identical to day 1.

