## 7.4 Justification for the use of placebo

The study is a crossover trial whereby all participants will receive one dose of nicotine and all participants will receive one dose of placebo. As this study is not designed to treat symptoms for a clinical benefit, we anticipate no potential harm that may come to the participant as a result of receiving placebo. Subjects will continue on their outpatient medications during this study.

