The guestion of development of physiological dependence or even nicotine use disorder secondary to patch exposure in non-smoking participants is an important one. The likelihood can be based on previous studies in non-smoking participants that were conducted for significantly longer periods of time than in the proposed study. Nicotine patch has been used for 4-weeks in patients with mild-moderate Alzheimer's Disease for 16 hours per day, initially using 5 mg patches for 7 days, 10 mg patches for 14 days, and finally 5 mg patches for 7 days. In general, patches were well tolerated, with only one of 8 subjects discontinuing. There were no observed nicotine withdrawal symptoms in these participants. Sleep interruption was not problematic as the patches were removed at bedtime. An almost identical study was performed with 15 subjects with ageassociated memory impairment using the same nicotine patch dose. Only one of 15 subjects withdrew from this study due to nicotine-related side effects, in this case, nausea. In this study, the most common side effects were local skin irritation, mild nausea and abdominal discomfort, and lightheadedness. Two subjects reported palpitations, but there was no change in body weight, blood pressure, or heart rate in subjects receiving nicotine compared to receiving placebo. No subjects appeared physiologically or psychologically dependent on the nicotine patches. In a 6-month trial of transdermal nicotine or placebo to treat mild cognitive impairment, no subjects (0 of 34 subjects) developed withdrawal or continued to use nicotine products following the study. Data from studies of smokers, who might be predisposed to difficulty discontinuing nicotine-containing products, demonstrated that difficulty with discontinuation of transdermal nicotine after use for smoking cessation was rare (2%), with the percentage of smokers continuing to use nicotine replacement products proportional to the rate of nicotine delivery. Taken together, these previous studies are reassuring regarding the safety of nicotine products from an addiction potential standpoint in non-smoking subjects.

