## 12 Statistical considerations

#### 12.1 Power analysis

Power analysis for error rates and reaction times is based on effect sizes from previous studies of the Emotional Go/NoGo task in subjects with schizophrenia and our preliminary data from a secondary analysis of a clinical trial of the alpha-7 nicotinic agonist GTS-21. With a sample size of 25 subjects, we will achieve 80% power at  $\Box$ lpha = 0.05 to detect a difference from 35% to 10% in the omission error between two experimental conditions within a subject (expected correlation of 0.60) and to detect an effect size of 0.6 in the mean reaction times between the control and intervention conditions within a person using paired t-test at alpha = 0.05. The dropout rate in a similar published acute crossover study of schizophrenia patients was ~15%. We thus anticipate needing to enroll 30 subjects to result in 25 completers for an appropriately powered study. We will match this group with a healthy control sample of similar size.

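### The standard side-effect questions are asked once, about the period after day 1, so no planned inquiry covers discharge after a day 2 patch or reaches subjects who do not return

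*Combined protocol and SAP*

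**What the plan says.** Section 6.2 sets two safety steps around the patches. On the testing day, "Subjects will be monitored for at least 30 minutes after patch removal to confirm the absence of side effects" that would make leaving the hospital unsafe. At the second visit, subjects are questioned about the first: "They will be asked a series of standard questions to assess for the presence of any side effects following their initial study day". For the rest of the second visit, "The remainder of the procedure will be identical to day 1", so the on-site observation applies on both days. No call, visit or questionnaire after day 2 is described.

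Section 7.4 states the design: "The study is a crossover trial whereby all participants will receive one dose of nicotine and all participants will receive one dose of placebo". Section 5.4 says "Treatment order will be block randomized by a member of the Center for Cognitive Medicine", without giving the allocation ratio.

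Other sections bear on safety collection:

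- Section 8.2.5: close monitoring by staff during the baseline assessment and both study days.
- Section 9.4: subjects can contact staff while enrolled and hold a study physician's contact details at all times.
- Section 10.1.2: adverse events are monitored for each subject. No method, schedule or end of collection is given.
- Section 10.1.6: the principal investigator reviews all adverse events when each subject completes.
- Section 11: a subject who withdraws without giving a reason is asked whether he or she would like to give one. The stated purpose is to improve retention.

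**The concern.** The two treatment periods are followed differently. After the day 1 patch, a returning subject is asked a standard set of questions covering about a week. After the day 2 patch, nobody is asked anything once they leave. Whether a nicotine exposure is followed by the questions therefore depends on the order drawn and on whether the subject comes back.

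The protocol itself names effects that could appear or persist after discharge. Section 8.1.1 lists skin irritation, nausea, headache, palpitations and dizziness. It also says that the question of dependence or nicotine use disorder "secondary to patch exposure in non-smoking participants is an important one", and takes reassurance partly from a six-month trial in which 0 of 34 subjects developed withdrawal or went on using nicotine afterwards. This study plans no comparable observation after a day 2 nicotine patch. The end-of-subject review in section 10.1.6 can then work only from events seen on site or volunteered.

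The crossover advantage is also lost for this information. The answers compare nicotine-first with placebo-first subjects, about 12 to 13 returning subjects in each order per group, instead of each subject with himself or herself.

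**Working it through.** **Inputs.** From section 12.1: 30 patients enrolled for 25 completers, about 15% dropout, and a healthy control group of similar size (taken here as also 30 and 25). From section 7.4: one nicotine and one placebo exposure per subject. Assumptions: 1:1 order, and all dropout falling between day 1 and day 2.

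**The plan's own figure.** 25 / (1 − 0.15) = 29.4, rounded up to 30. This reproduces the stated enrolment. Five lost of 30 is 16.7%.

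**Counting exposures.** Let N subjects be dosed on day 1, half of them nicotine-first. Let a be the nicotine-first dropouts and b the placebo-first dropouts.

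- Nicotine exposures = N/2 + (N/2 − b), because placebo-first dropouts never receive nicotine.
- Exposures followed by the questions = N/2 − a.
- Not followed = (N/2 − b) + a.

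**Both groups together, N = 60, 10 dropouts.**

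| Dropout pattern | Nicotine exposures | Followed by the questions | Not followed |
|---|---|---|---|
| Even (a = 5, b = 5) | 30 + 25 = 55 | 25 | 30 (54.5%) |
| All placebo-first (a = 0, b = 10) | 30 + 20 = 50 | 30 | 20 (40.0%) |
| All nicotine-first (a = 10, b = 0) | 30 + 30 = 60 | 20 | 40 (66.7%) |
| None (a = b = 0) | 60 | 30 | 30 (50.0%) |

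With an equal dropout rate d in both orders, the share not followed is 1 / (2 − d). At d = 0.15 this is 1 / 1.85 = 54.1%.

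**If the order is not 1:1.** Take one group of 30 with 5 dropouts shared in proportion to the orders. With 60% nicotine-first there are 28 nicotine exposures and 15 followed, leaving 13 of 28 = 46.4%. With 40% nicotine-first there are 27 exposures and 10 followed, leaving 17 of 27 = 63.0%.

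**What silence would tell us.** With zero events among n subjects asked, the one-sided 95% upper bound on the rate is 1 − 0.05^(1/n).

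- n = 25 (asked under the plan, even dropout): 11.3%.
- n = 55 (all nicotine exposures asked): 5.3%.
- n = 34 (the trial cited in section 8.1.1): 8.4%.

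**The case against.** The strongest reply is that little is likely to be missed. The task begins at the latest 120 minutes after patch placement and lasts about 12 minutes, after which the patch comes off. Section 8.2.1 expects discomfort to subside shortly after removal, and subjects are watched on both days. On dependence, section 8.1.1 goes on to cite much longer exposures in non-smokers and finds them reassuring. A study of this size could not exclude uncommon delayed effects even with full questioning. All of this stands and limits the severity of the point.

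Several stronger readings are tempting, and the documents do not support them.

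- **Post-discharge effects go wholly unmonitored.** Sections 9.4, 10.1.2, 10.1.6 and 11 leave passive contact, a general monitoring statement, a review of recorded events and an optional reason for withdrawal. What is missing is a planned, structured inquiry.
- **Non-returners are the people who felt worst.** This is plausible but undocumented. Sections 6.1 and 9.2 suggest other influences on return: transport, time off work, and the $100 paid only after the second testing visit.
- **Psychiatric exacerbation is an unobserved nicotine risk.** Section 8.2.2 ties it to stressful experiences in assessments and tasks, and calls it very unlikely.
- **A planned safety comparison is biased.** Section 12.2 plans models for omission errors and reaction time only. A comparison of the day 1 answers between orders would be small but randomised, apart from dropout.
- **The denominator is all 60 enrolled.** If dropout is evenly split after day 1, 5 placebo-first subjects never receive nicotine, so it is 55.

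**Conclusion.** The gap is real and modest. Followed exactly, the plan never solicits post-discharge effects of a day 2 patch, or of any patch in a subject who does not return. On the plan's own sample size, with 1:1 order and evenly split dropout after day 1, that is 30 of 55 nicotine exposures (55%). The share depends on those assumptions. It is 50% with no dropout, and it falls below half if dropout is mainly placebo-first (40% at the extreme) or if clearly more than half are allocated nicotine first. It reaches 67% if all dropouts are nicotine-first. A clean record among the 25 asked would exclude only rates above 11.3%, against 5.3% for 55. The primary outcomes and their analysis are not affected. This is an inexpensive improvement to safety collection and does not call the trial's main conclusions into question.

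**What to change.** In section 6.2, add one short telephone call to every subject who received any patch, including those who do not return. Make it at about the same interval after the last patch as the gap between the two testing days (about one week, and not under 5 days). Use the same standard questions as at the day 2 visit, and add to both occasions an item on nicotine or tobacco use since the patch. In section 10.1, name these two inquiries as the collection method and state when collection ends for each subject. Tabulate the answers by treatment, with equal windows after each patch, and report how many exposures were followed by an inquiry.

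The cost is protocol wording and about 60 short calls by existing staff over the four-year data collection phase. Slightly more events will be reported, and some non-returners will not be reached. Telephone answers may also differ somewhat from those given in person. Nothing changes in the treatment, the testing visits or the primary analysis.

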## 7 Study drug

#### 7.1 Background

Please see section 3.2 for a description of acute transdermal nicotine use in humans for cognitive and behavioral outcomes.

#### 7.2 Drug source

Nicotine patches will be purchased from a commercial source and provided to subjects free of charge. The investigators will provide the study drug through project funding by the National Institutes of Health and Vanderbilt University Medical Center Department of Psychiatry and Behavioral Sciences.

#### 7.3 Storage, preparation and use

Nicotine patches will be stored according to manufacturer's instruction. Prior to use, all patches will be covered with surgical tape. Patches will be prepared by an unblinded staff member of the Vanderbilt Center for Cognitive Medicine (CCM) who is not affiliated with the study but is responsible for drug randomization. For subjects who are to receive active drug on that day, the backing will be peeled off the patch and affixed to the subject's arm and sealed in place by surgical tape. For subjects who are to receive placebo on that day, the backing will be *not* be peeled off the patch, and the patch will be affixed to the subject's arm and sealed in place by surgical tape. The CCM staff member will affix the patch in all cases, in general to the upper arm so that the patch will subsequently be hidden below sleeves.

## 7.4 Justification for the use of placebo

The study is a crossover trial whereby all participants will receive one dose of nicotine and all participants will receive one dose of placebo. As this study is not designed to treat symptoms for a clinical benefit, we anticipate no potential harm that may come to the participant as a result of receiving placebo. Subjects will continue on their outpatient medications during this study.

## 8 Risks, minimizing risks, and potential benefits

## 8.1 Risks

The reasonably foreseeable risks to subjects in this study include a) study medication, b) psychological and behavioral assessments, and c) breach of data security and privacy. There may also be unknown or unanticipated adverse effects.

## 8.1.1 Study medication: transdermal nicotine

Side effects of transdermal nicotine exposure have been well characterized, and participants may experience nausea, headache, skin irritation, palpitations, and dizziness. These side effects were found to be dose related in healthy, non-smoking subjects, with 15 mg nicotine patch significantly less likely to cause side effects than higher dose such as 30 mg. Specifically, in this study 8 non-smoking patients were given a 15 mg nicotine patch. Five of 8 patients experienced mild nausea and lightheadedness after one hour, while 3 of 8 did not have any side effects. Seven of 8 patients continued with the study. Other studies have demonstrated that development of nicotine side effects is highly related to rate of increase and peak concentration of plasma nicotine. Studies of chronic transdermal nicotine in non-smoking populations are very encouraging regarding tolerability. In a large study of transdermal nicotine for treating mild cognitive impairment in older adults, tolerability was excellent in the over 30

subjects randomized to nicotine treatment. Transdermal nicotine use has been successfully reported in case series or trials of patients with advanced dementia and age, a population that is likely to be increasingly sensitive to nicotine than younger, healthier subjects in this study.

The guestion of development of physiological dependence or even nicotine use disorder secondary to patch exposure in non-smoking participants is an important one. The likelihood can be based on previous studies in non-smoking participants that were conducted for significantly longer periods of time than in the proposed study. Nicotine patch has been used for 4-weeks in patients with mild-moderate Alzheimer's Disease for 16 hours per day, initially using 5 mg patches for 7 days, 10 mg patches for 14 days, and finally 5 mg patches for 7 days. In general, patches were well tolerated, with only one of 8 subjects discontinuing. There were no observed nicotine withdrawal symptoms in these participants. Sleep interruption was not problematic as the patches were removed at bedtime. An almost identical study was performed with 15 subjects with ageassociated memory impairment using the same nicotine patch dose. Only one of 15 subjects withdrew from this study due to nicotine-related side effects, in this case, nausea. In this study, the most common side effects were local skin irritation, mild nausea and abdominal discomfort, and lightheadedness. Two subjects reported palpitations, but there was no change in body weight, blood pressure, or heart rate in subjects receiving nicotine compared to receiving placebo. No subjects appeared physiologically or psychologically dependent on the nicotine patches. In a 6-month trial of transdermal nicotine or placebo to treat mild cognitive impairment, no subjects (0 of 34 subjects) developed withdrawal or continued to use nicotine products following the study. Data from studies of smokers, who might be predisposed to difficulty discontinuing nicotine-containing products, demonstrated that difficulty with discontinuation of transdermal nicotine after use for smoking cessation was rare (2%), with the percentage of smokers continuing to use nicotine replacement products proportional to the rate of nicotine delivery. Taken together, these previous studies are reassuring regarding the safety of nicotine products from an addiction potential standpoint in non-smoking subjects.

#### 8.1.2 Psychological assessments and Emotional Go/NoGo task

At screening, subjects will undergo non-invasive psychological assessment of a structured nature that has been consistently used without adverse effects in previous studies with a similar subject population. On testing days, subjects will perform the Emotional Go/NoGo task to measure impulsivity in an emotional context, a behavioral construct related to impulsive aggression. This task has been administered to healthy controls as well as patients with schizophrenia without report of adverse events. There is the potential risk that subjects may become fatigued during the performance of screening assessments or behavioral tasks, and that discussion of personal issues with study personnel in the context of screening issues may be stressful or uncomfortable. Because subjects participating in this study will be stable outpatients, it is unlikely that the stress posed by such measures will exacerbate baseline psychiatric symptoms.

## 8.1.3 Electroencephalography (EEG)

Subjects will undergo (EEG) using an EEG cap while performing the emotional Go/NoGo task. The risks of EEG are minimal and include risk of mild discomfort while wearing the EEG cap.

## 8.2 Minimizing Risks

## 8.2.1 Risk of study medication

Dependance: Please see above for a discussion regarding the risk of development of dependence. We chose transdermal delivery of nicotine because its slow rate of delivery significantly reduces the risk of dependence development.

Discomfort: The potential for discomfort will be clearly explained to subjects. Subjects experiencing discomfort who wish to have the patch removed will immediately have their patch removed, and symptoms will subside shortly thereafter. Placebo patches will be handled in exactly the same manner, with the same ability to remove as described above. It should be noted that nicotine patches have been used successfully in populations with cardiovascular disease. Although subjects with known cardiac conduction abnormalities or poorly treated hypertension as assessed during screening will be excluded, these data are reassuring given the possibility of enrolling a subject with a previously undiagnosed cardiovascular condition.

## 8.2.2 Risk of psychological assessments and Emotional Go/NoGo task

The primary protection against risk for this aspect of the study is the continuous explanation of study procedures, the reasoning for their use, ongoing confirmation that subjects understand these explanations, and consistent communication of the voluntary nature of the study. While it is very unlikely, there is always the theoretical risk of exacerbation of psychiatric symptoms in individuals with schizophrenia due to stressful experiences. Again, a thorough understanding of assessments and behavioral tasks mitigates this risk. The use of standardized Subject Monitoring and Emergency Procedures, described below, will further guard against harm to subjects in the event of exacerbation of psychiatric symptoms.

## 8.2.3 Electroencephalography (EEG)

The risks of EEG are minimal. Potential discomfort of wearing the EEG cap will be minimized by ensuring the correct fitting on the subject's head.

## 8.2.4 Risk of breach of data security and privacy

Data obtained from human subjects will be confidential and accessed only by members of the study team with appropriate IRB and HIPAA training, as assured by standard training protocols at VUMC. Data is maintained and secured in locked file cabinets or on encrypted, password protected computers, located in locked offices, and following Health Insurance Portability and Accountability Act (HIPAA) guidelines and the policies and procedures of VU and VUMC. Individuals will be identified by a numerical code that will be kept separate from study data.

#### 8.2.5 Subject Monitoring and Emergency Procedures

Throughout the baseline assessment and two study days subjects are closely monitored by an experienced clinical research team, under the supervision of [name]. Subjects performing the Emotional Go/NoGo task and electroencephalographic recording will be monitored by at least one member of the research team. All members of the research team are familiar with the established VU/VUMC emergency plans in the case of a medical or psychiatric emergency. In the case of a medical emergency, a medical response team at VPH will provide immediate first aid and if deemed necessary, emergency medical services will be called by the VPH staff. VUMC's Emergency Department is located one block away from VPH enabling rapid medical care. In the case of a psychiatric emergency, a crisis response team at VPH will respond, which has extensive training in crisis situations. Further crisis evaluation can be performed at VPH or VUMC Emergency Department, and though extraordinarily unlikely, inpatient psychiatric care can be provided through VPH. [name] is a credentialed attending physician at VPH and can help arrange for this level of treatment should the need arise.

